**Figure 9 – Preliminary results for Aim 1.** Using different configurations of artificial neural networks, we can achieve very high accuracies. In this case, a 1-layer combination of two large 2-layer networks for each axis provided the best results (bolded above).

greater sensitivity than our single-axis networks. But we do not have concurrent VF validation of the data obtained from the healthy people. Collection and analysis of these data will complete the range of swallow function and enable completion of our 2nd and 3rd aims, which seek to develop an HRCA impairment severity continuum.

**A1.d. Experimental approach:** STEP 1: We will collect concurrent VF and HRCA recordings from 70 healthy subjects (35 females and 35 males) with no previous history of swallowing difficulties who are age matched to our database of swallows from patients with OPD. Each subject will complete five swallows of 3mL thin liquid and five swallows of self-selected, comfortable volume of thin liquid from a cup, in a head-neutral position. STEP 2: We will first measure nine kinematic measures with VF (onset, offset, and time to peak hyolaryngeal excursion; laryngeal closure and reopening; UES closure and reopening; onset and offset of tongue base to posterior wall contact), penetration-aspiration scale scores [109], and pharyngeal retention/residue scores [89, 110, 111, 112].

STEP 3: Pre-process all HRCA recordings per steps taken in previous publications [29, 30, 71], to remove any disturbances and diminish noise in these recordings. STEP 4: VF results (STEP 2) will be equated with HRCA signal features and categorized by bolus volume of the swallowed material, these data will be combined with the data from over 4000 patient swallows from our previous R01 grant.

[figure not shown]

Figure 10 – Our proposed experimental and data analysis approach for Aim 1.

STEP 5: We will develop an algorithm based on the state-of-the-art machine learning concepts that will differentiate between healthy controls and people with suspected OPD whose swallows did not exhibit OPD (see Figure 10). Specifically, we will analyze a random 70% training subsample and use the deep belief machine learning approach as in our preliminary work [70]. Once modeling is complete, the remaining 30% validation subsample will be used to obtain accuracy estimates devoid of model overfitting.

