**A1.e. Data interpretation:** In STEP 2, [name] will train doctoral students to evaluate all VF dependent variables and establish their inter- and intra-rater reliability (intraclass correlation coefficient above 0.9 for continuous variables and kappa above 0.75 or percent exact agreement above 80% for categorical variables), in the measurement of kinematic event timing, and assignment of P-A and pharyngeal retention/residue scores. They will use ImageJ image processing software, to measure penetration-aspiration scores, and kinematic and pharyngeal retention/residue measures from all swallow recordings in this new set of healthy swallows, and complete the same measurements from the remaining 3900 swallows in our database that did not undergo the complete kinematic analysis that we performed to produce the preliminary data presented in section A2.c. To ensure their judgments do not drift over time, we will perform ongoing reliability measures using the same criteria, through a rolling re-analysis of a randomly selected 10% of analyzed swallow recordings. Then, to understand the accuracy of the developed HRCA analysis algorithm using only the training subsample in STEP 5, we will begin by calculating a confusion matrix [85]. The confusion matrix will be calculated by comparing the algorithm's output with scores from STEP 2. The confusion matrix will be then used to calculate false positives, false negatives, true positives and true negatives, and lastly sensitivity, specificity, predictive values and likelihood ratios for the algorithm. These values will be initially calculated using the leave-one-out approach, but we will then repeat the analysis with 10-fold cross-validation. Then in STEP 5, we will use the number of correctly and incorrectly HRCA-detected swallows to calculate the sensitivity and specificity values, again using the leave-one-out approach (the most exhaustive and computationally expensive cross-validation approach) and 10-fold cross-validation. We have proposed state-of-the-art machine learning methods based on deep learning as our primary analysis, but we will also consider other techniques such as classification tree methods [113], and generalized linear models due to their ability to produce simpler prediction rules for ease of use, cognizant of the potential loss of some accuracy compared to deep learning. Finally, we will use the validation subsample to obtain authoritative measures of accuracy devoid of risks of model overfitting.

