
**A1.f. Expected outcomes:** The benchmark for success of Aim 1 will be creation of a machine learning algorithm that completes the continuum of of HRCA signal characteristics from normal to the most severely impaired swallowing function that will then be available for future research. Specifically, we anticipate these algorithms

will correctly identify normal airway protection (PAS scores of 1-2) in healthy controls and patients with dysphagia with over 90% accuracy compared to the gold standard VF ratings for each swallow [70]. These outcomes will establish the evidence that the HRCA signals and advanced analytics form a robust and reliable swallowing screening system with comparable accuracy to VF, while also demonstrating the system's ability to identify additional swallowing diagnostic features that are currently only possible with VF, potentially advancing HRCA as not a screening tool with diagnostic capabilities far beyond SIS.

**A1.g. Challenges and contingency plans:** The preliminary results (see A1.c.) strongly support our hypothesis (see A1.a.). In the highly unlikely event that our VF judges' ratings drift unacceptably, we will increase surveillance on inter- and intra-rater reliability and pull judges from analysis and retrain them to criterion, retest their reliability before placing them back online.

**A1.h. Sample size justification:** We currently have data on 4000 swallows from 274 dysphagic persons. We plan to add 700 swallows from 70 healthy persons to this data set. Allowing for some refusals, we anticipate obtaining 650 swallows from 65 healthy persons. Assuming the sensitivity and specificity will be approximately 90%, intra-class correlation of 0.7 from our prior data and a resulting design effect of 3.8 [114], and using published methods [115, 116] implemented in commercially available software (PASS 2012, Number Cruncher Statistical Systems, Kaysville, UT), conservatively we will be able to estimate sensitivity with a margin of error as small as  $\pm 2\%$  and specificity with  $\pm 8\%$  in the training sample, and  $\pm 3\%$  and  $\pm 13\%$  in the validation samples, at the 95% confidence level.

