kinematic events (onset of barium entering pharynx, onset, offset and arrival at maximum displacement of the hyoid bone, onset and offset of laryngeal closure, onset of laryngeal reopening, onset and offset of UES opening, onset of UES reclosure, onset and offset of contact of the tongue base to the posterior pharyngeal wall, and first re-opening of tongue base to posterior pharyngeal wall contact) were measured by judges who were trained in VF image processing methods, blinded to patient diagnosis, and whose inter- and intra-rater reliability were acceptable. The results were compared to HRCA signals to determine the frequency of occurrence of 7 separate HRCA signal feature peaks (maxima) with each of the 13 swallow kinematic events, to a tolerance of within 0.1 seconds of the actual swallow kinematic events, the standard tolerance for temporal VF analysis [89], (Table 2). Fifty-two to 88% of the kinematic events were detected within this tolerance by HRCA sensors more than half of the time. Since the probability is <8% that any continuous vibratory or acoustic signal would exhibit a strongly systematic change that co-occurs with specific swallow kinematic events, these findings indicate that HRCA signal features are strongly associated with swallow kinematic events and may show promise in identifying abnormal vs. normal swallow function. We then stratified the data into two PAS score ranges: 1-2 (normal airway protection) and 3-8 (abnormal airway protection). Microphone and accelerometer signal feature peaks co-occurred with normal airway protection 40-49% of the time, but these peaks co-occurred only 11-14% of the time during abnormal airway protection swallows. Moreover, the ranges of these probabilities did not overlap for any of the four data collection channels, and the results were statistically significant as expected at  $p=0.018$ . These results indicate that HRCA can detect co-occurring swallow kinematic events while at the same time differentiating between normal and abnormal airway protection. Though these results indicate HRCA's ability to detect simultaneously occurring swallowing events and airway compromise in the presence of other noise, the necessary next step is to equate this capability to standard measures of overall swallow impairment.

[figure not shown]

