### **A3.c. Justification and feasibility – Preliminary studies:**

In our initial study [31], we collected time-linked HRCA signals and VF, using a protocol of three sips of thin liquid barium (5 cc each). The classification algorithms were trained to discriminate swallows with PAS scores of 1 and 2 (safe) from those with scores  $\geq 3$  (penetration of material into the airway, above the level of the vocal cords, without clearance) and succeeded in this task at the level of the single bolus with 90% sensitivity and 77% specificity.

[figure not shown]
When all the swallowing tasks performed by each patient were considered in aggregate, sensitivity for the detection of aspiration (i.e., anywhere in the protocol) improved to 100%, but specificity fell to 54%. These details are summarized in Table 4. Next, [name] has used HRCA signals collected from 30 older adults [101] to develop a support vector machine classifier to distinguish between grossly safe and unsafe swallowing with high sensitivity ( $97.1 \pm 2\%$ ) and modest specificity ( $64 \pm 8.8\%$ ). Also, we used HRCA signals from 29 pediatric participants along with a support vector machine classifier to achieve an adjusted accuracy of  $89.6\% \pm 0.9$  for the discrimination between swallows with and without airway entry [102]. Most recently, [name] has used a Bayes’ machine learning approach to infer about the airway protection in 40 patients with dysphagia [105]. This was the first study that demonstrated that we can grossly differentiate healthy swallows (P-A scores  $\leq 3$ ) from penetration-aspiration swallows (P-A scores 4-8) with an accuracy greater than 90%. These preliminary results demonstrate that we can reliably differentiate safe and unsafe swallowing events.

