### **A3.d. Experimental approach:** The main goal of this aim is to demonstrate that the proposed HRCA tool is objective and can improve upon the accuracy of SIS alone in identifying participants who have OPD and need to undergo a VF exam or need immediate intervention (Figure 11). To achieve this goal, we will carry out the following experimental steps:

STEP 1: Enroll 50 consenting patients eligible for SIS in the experiment, and perform combined SIS screening and an HRCA screening. STEP 2: The HRCA system will be applied to all patients. The dysphagia SIS screen employed in the University of Pittsburgh Medical Center Presbyterian University Hospital will be performed, which consists of two or three 5mL water swallows and drinking 90mL of water at a self-selected pace. STEP 3: Nurses or other staff (non-SLPs or physicians) administering the screens and blinded to the HRCA output, will score the screens on the basis of the institutional SIS algorithm, denoting any signs of OPD or penetration/aspiration (e.g., wet voice, coughs) for each swallow that is observed. For the concurrent HRCA screening, we will record and denote the output of the algorithm for each observed swallow with findings from Aims 1 & 2. STEP 4: We will administer a VF exam for all patients using clinical protocols that include the same bolus conditions (5mL thin liquid, 30mL thin liquid) of swallowed material used in the SIS, within a 24-hour period to confirm the presence or absence of dysphagia/aspiration. STEP 5: The MBSImP, the PAS and the Normalized Residue Ratio Scale will be used to measure swallow impairment, airway protection and post-swallow pharyngeal residue. These measures will be made by our trained laboratory associates. STEP 6: HRCA, SIS, and VF results will be compared.

**Table 4 –** HRCA-based screening can detect aspiration, validated against concurrent VF. SENS = Sensitivity; SPEC = Specificity; FPR = False Positive Rate; FNR = False Negative Rate; PB = Per bolus; PP = Per participant.

Parameter	Statistic	PB	PP
Impaired Swallowing Safety (13/40 patients; 55/154 swallows)	SENS	90%	100%
	SPEC	77%	54%
	FPR	23%	48%
	FNR	10%	0%

**Figure 12 –** Our proposed experimental and data analysis approach for Aim 3.

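### Aim 1 trains on a healthy-versus-patient label but is scored against each swallow's videofluoroscopy rating, and the Aim 2 modelling step repeats the Aim 1 target

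*Combined protocol and SAP*

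**What the plan says.** **Training target, Aim 1 (A1.d, STEP 5).** The algorithm is to "differentiate between healthy controls and people with suspected OPD whose swallows did not exhibit OPD". A random 70% of the data is used for training and 30% for validation.

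**Scoring, Aim 1 (A1.e).** The confusion matrix compares the algorithm's "output with scores from STEP 2". The STEP 2 scores are kinematic timings, PAS and pharyngeal residue, all read from VF. Sensitivity, specificity, predictive values and likelihood ratios follow from that matrix.

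**Expected result, Aim 1 (A1.f).** The algorithms "will correctly identify normal airway protection (PAS scores of 1-2) in healthy controls and patients with dysphagia with over 90% accuracy", with the VF rating of each swallow as reference.

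**Precision, Aim 1 (A1.h).** The section says "conservatively we will be able to estimate sensitivity with a margin of error as small as" ±2% in training and ±3% in validation. For specificity it gives ±8% and ±13%. It assumes 90% for both measures, an intra-class correlation of 0.7 and a design effect of 3.8.

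**Aim 2.** STEP 5 of A2.d again gives as output the split between healthy controls and patients whose swallows showed no dysphagia, followed by a stray pair of words. A2.a, A2.e and A2.f instead call for models of MBSImP, PAS and residue, assessed by R² and root mean square error.

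**The concern.** In STEP 5 both classes consist of swallows without OPD; what separates them is who swallowed. The scores used in A1.e do not record that. The expectation in A1.f pools the two groups and asks only whether airway protection was normal. A PAS 1-2 swallow from a healthy control and one from a patient can thus be opposites for training and identical for scoring.

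Followed literally, the Aim 1 accuracy figures would be computed against a reference that the classifier was not trained to predict. If only the two STEP 5 groups are scored, and not exhibiting OPD implies PAS 1-2, the patient class supplies no VF-abnormal swallow and sensitivity against VF has essentially nothing behind it. Two analysts could train and score different classifiers from the same text and reach different conclusions about Aim 1, with the choice of label open until results are seen.

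In Aim 2 the conflict needs no assumption: a healthy-or-patient output cannot be turned into ordinal MBSImP, PAS or residue scores.

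**Working it through.** **1. Labels side by side**
- Healthy control, PAS 1-2: class healthy in STEP 5; normal in A1.f.
- Patient, PAS 1-2, no OPD: class patient in STEP 5; normal in A1.f.
- Patient, PAS 3-8: presumably outside the STEP 5 contrast, which states no PAS cut; not normal in A1.f.

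The second line is the conflict. The third shows that STEP 5 gives no rule for swallows with OPD.

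**2. Where the 90% comes from.** A1.f supports its figure with the group's own deep belief network pilot. A1.c describes that pilot as separating healthy swallows from the least impaired patient swallows, with a best accuracy of 91.3%, and concedes that the healthy data had no concurrent VF. A group-label result is being used to support a VF-label expectation.

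**3. Illustration of the mismatch.** Inputs from A1.h: 650 healthy and 4000 patient swallows, 4650 in all. Let g be the share of patient swallows in the STEP 5 patient class. Assume all healthy swallows and all swallows in that class are PAS 1-2, an output of patient is read as PAS 3-8, STEP 5 is perfect, and every other swallow is called correctly. Then

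accuracy against PAS = (650 + 4000(1 − g)) / 4650.

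- Above 90% requires 4000g < 465, so g < 11.6%.
- g = 25% (assumed): 3650/4650 = 78%.
- g = 75% (assumed): 1650/4650 = 35%.

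**4. The A1.h margins.** Half-width = 1.96 × √(0.90 × 0.10 × 3.8 / n), with n the number of positive swallows.
- Plan's figure: all 4000 patient swallows positive, n = 2800 and 1200, gives 2.2% and 3.3%. This matches ±2% and ±3%.
- To round to 3% in validation the half-width must be below 3.5%, so n > 0.342 × (1.96/0.035)² = 1073, or about 89% of the 1200.
- Positives are the VF-impaired swallows, assumed 75% of patient swallows: n = 2100 and 900, giving 2.5% and 3.8%.
- Assumed 25%: n = 700 and 300, giving 4.3% and 6.6%.

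The stated sensitivity margins therefore fit a third target, nearly all patient swallows against healthy ones. STEP 5 takes as its patient class only the patient swallows without OPD, and A1.f counts as abnormal only those outside PAS 1-2.

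**The case against.** The case for reading the plan more kindly has weight. The STEP 5 contrast is deliberate: the Aim 1 hypothesis and A1.a want healthy swallows distinguished from those of patients. A1.f names as its benchmark an algorithm covering the whole continuum; the PAS figure follows as something anticipated of algorithms in the plural. STEP 2 scores may have been meant to select the patient swallows without OPD. Figures 10 and 11 might show more than two classes. In Aim 2, everything except STEP 5 of A2.d agrees, so that sentence looks like a copying slip. In A1.h the wording suggests a best case, although the same sentence also calls it conservative.

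This stands as far as intent goes. It does not remove the conflict, because the text describes one classification target in Aim 1 and A1.e scores that algorithm against VF.

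Some stronger inferences should be resisted:
- A reader might conclude that the contrast itself is wrong. It is a fair test of the Aim 1 hypothesis.
- A reader might think the specificity margins do not reproduce, since 650 swallows at design effect 3.8 give 5.4% and 8.2%. They do reproduce on one bolus condition: 65 × 5 = 325 swallows, design effect 1 + 4 × 0.7 = 3.8, exact binomial half-widths 8.4% and 13.3%. The text does not state that basis.
- A reader might see two PAS cuts, because A3.c separates scores up to 3 "from penetration-aspiration swallows (P-A scores 4-8) with an accuracy greater than 90"%. That describes a previous 40-patient study. A1.f uses 1-2, and so does the split in A2.c: "We then stratified the data into two PAS score ranges: 1-2 (normal airway protection) and 3-8 (abnormal airway protection").

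**Conclusion.** The target and the reference do not match in Aim 1, and STEP 5 of A2.d does not match the rest of Aim 2. This should be fixed before modelling begins.

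The 78% to 35% range illustrates the mismatch and does not predict performance. It depends on equating patient with PAS 3-8, which the plan never states, and on an assumed g. A reader might take g from Table 4 ("Impaired Swallowing Safety (13/40 patients; 55/154 swallows"), where 99/154 = 64% of swallows were unimpaired, and conclude that accuracy is capped at 45%. That table comes from another sample of 40 patients swallowing thin liquid and does not give g for this database.

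The sensitivity margins of ±2% and ±3% hold only if nearly all 4000 patient swallows count as positive. On VF-impaired swallows they are about ±2.5%/±3.8% to ±4.3%/±6.6% for an assumed 75% to 25% impaired, keeping the plan's design effect.

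A reader might also infer that the Aim 3 trial is compromised. The documents do not show this: A3.d, STEP 3, does not name which algorithm output is carried forward, and the logistic models in A3.e are fitted against the presence of clinically significant OPD or aspiration, so they may avoid the problem.

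**What to change.** 1. **A1.d, STEP 5.** Keep the contrast as the test of the Aim 1 hypothesis. Define absence of OPD by an explicit rule on the STEP 2 scores, and score this classifier on group membership.
2. **A1.e and A1.f.** For the 90% figure, train and score a separate classifier on each swallow's VF label, PAS 1-2 against 3-8, with healthy and patient swallows pooled. Also report its accuracy within patient swallows alone, because the source of a recording partly predicts its label.
3. **A2.d, STEP 5.** Replace the two-group target with the MBSImP, PAS and residue scores of STEPS 1 to 3.
4. **A1.h.** State which swallows are positive and which negative for each classifier, and restate the sensitivity margin on that basis.

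The cost is wording, one more classifier and a recalculation, with a less favourable stated sensitivity margin. No new data are needed, since A1.e already plans VF measurement of the healthy swallows and of the database swallows not yet fully measured.
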